## 16.0 Confidentiality

### Data Security:

16.1 All participants will be identified by a research identification number. All research data will be de-identified using ID numbers. Hard copies of documents will be stored in a locked cabinet. The participants name will be retained on consent and assent forms and these forms will be stored in a separate, locked cabinet. Both cabinets will only be accessible to the research team on the protocol. Behavioral and clinical data will be entered electronically using the ID numbers onto the HIPAA-compliant REDCap database that is managed by the University of Minnesota. Clinical data and questionnaires may be completed using REDCap or paper documents. Raw behavioral and EEG/ECG data will be stored on the HIPAA-compliant Box Secure Storage. Data may also be stored on password protected databases and files on AHC-IS servers (cnc2.med.umn.edu). De-identified neuroimaging data will be stored locally on servers supported by the Center for Magnetic Resonance (CMRR). Access to these electronic directories will be limited to the research staff. Copies of the consent form and other research study information will not be included in their medical, employment, or educational records to maintain confidentiality.

### **17.0** Provisions to Monitor the Data to Ensure the Safety of Participants

17.1 Data Integrity Monitoring: The principal investigator and/or co-investigator will monitor data quality for this study. They will ensure that data are generated, documented (recorded), and reported - in compliance with this

protocol, with Good Clinical Practice, and any other applicable regulatory requirements. Data will be stored in de-identified format. Study staff will monitor side effects forms and the CSSR-S for safety upon collection. Confidentiality may be broken in situations such as active suicidal ideation or other situations required by law.

17.2 Data Safety Monitoring. During all stimulation sessions, a member of the research staff will constantly monitor participants to ensure comfort and safety. A licensed clinical psychologist ([name]) or a supervising psychiatrist ([name]) will be contacted in the case of a clinical emergency to determine whether intervention is necessary. Emergency incidents will be documented and reported to the IRB. Documentation will include a description of the incident, action taken, and individuals involved. A 0 (No adverse event or within normal limits) to 5 (Fatal adverse event) rating scale will be used to evaluate the severity of adverse events and a 0 (Unrelated: The adverse event is clearly not related to investigational agent(s)) to 5 (Definite: The adverse event is clearly related to investigational agent(s)) will be used to determine the relationship between the adverse event and the proposed intervention. Any events rated 2 or higher will result in a notification to the supervising psychologist and events rated 3 or higher may warrant breaking the blind. Intervention will be determined by the supervising psychologist. Examples of incidents requiring immediate intervention and discontinuation from the study include active suicidal or homicidal ideation with plan, current self-harm requiring medical intervention, and a seizure. Data and safety monitoring will be discussed during weekly staff meetings with members of the research team to ensure that all adverse events are reported in compliance with the protocol, Good Clinical Practice, and other applicable regulatory requirements.

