- We will use a questionnaire to assess perceptions of tDCS treatment.

- Columbia-Suicide Severity Rating Scale (C-SSRS) assesses the presence and severity of suicidal ideation and behavior (Posner et al., 2011). The C-SSRS will be clinician administered with the participant by trained research staff and overseen by a licensed psychologist. Answers will be reviewed by trained clinical assessors who are supervised by a licensed psychologist. This will be administered at baseline for inclusion criteria, at the interim visit, at the post-tDCS and at final assessment visits to monitor suicidality.
- Inventory of Depression and Anxiety Symptoms (IDAS) assesses symptoms of depression and anxiety (Watson et al., 2007).
- Positive and Negative Affect Schedule (PANAS) is a mood scale that assesses positive and negative affect (Watson, Anna, & Tellegen, 1987). This will be administered at the beginning of each tDCS session and before and after each MRI and EEG session as a manipulation check and to assess participant mood at the end of the scans to ensure participants are not leaving sessions in a distressed mood. A study investigator will be contacted if the participant endorses a 5 ("Extremely") for being "upset," "guilty," "distressed," or "ashamed" at the end of the session.
- Dysfunctional Attitude Scale (DAS) assesses maladaptive beliefs associated with depression (Weissman & Beck, 1978)
- Action and Acceptance Questionnaire II assesses psychological inflexibility and experiential avoidance (Bond et al., 2011).
- Pittsburgh Sleep Quality Index (PSQI) assesses sleep quality (Buysse, Reynolds, Monk, Berman, & Kupfer, 1989).
- Cash Choice Task is a single-item survey assessing delay of gratification, impulsivity, and motivation (Wulfert et al., 2002).
- Participants will be asked at the beginning of each intervention session to rate the degree of rumination they experienced the day before. At the end of each MRI scan and EEG scan, participants will be asked to rate the degree of rumination they experienced during each scan (e.g.,

resting scan). They will rate the quality of mindfulness, rumination, neutral thinking, and rest, thoughts, and mood after respective EEG, MRI, and tDCS task completion.

- At the end of each intervention session and when they engage in MBT for the EEG and the MRI, participants will be asked to rate how successful they were at engaging in the MBT (see attached).

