- Participants will then be randomly assigned to one of two conditions: active tDCS + MBT and sham tDCS + MBT. Participants will undergo 10 daily sessions of tDCS across two weeks (visits 4-13). Missed sessions may be rescheduled. If there is a month or longer delay between the last baseline assessment visit (e.g.,

initial assessment, EEG, or MRI), participants may be asked to repeat some or all of the baseline research visits and will be paid accordingly.

- 4) Following the treatment, participants will complete a post-tDCS MRI scan, EEG/ECG session, and assessment visits (visit 14-16) that will include behavioral and cognitive assessments as well as questionnaires.
- 5) Participants will then complete 15 sessions of MBT either at home or in-person (only if the study team determines that it would be helpful for the participant to complete these sessions in-person) across 3 weeks. After they complete the home-based MBT training, all participants will complete a final EEG/ECG session and final assessment (visits 17 and 18), irrespective of how many athome/in-person MBT sessions were completed.

In total, this study will require 18 in-person visits and 20 online MBT sessions that can be completed at home (see Figure 1 for an overview of study activities). For participants who complete the 3-weeks of MBT in-person, there will be an addition of 15 in-person visits and a total of 4 online MBT sessions.

**Randomization:** A randomized block design will be used to assign each subject to undergo either active or sham tDCS in a 1:1 ratio. Randomization will occur after completion of the 5 at-home MBT sessions before their first tDCS + MBT laboratory visit.

5.4 Study Duration: The total duration of research activities for individual participants will involve 18 in-person visits and 20 MBT sessions that can be completed at home or in person (only if the study team determines that it would be helpful for the participant to complete these sessions in-person). Research-related activities will occur over the duration of up to 10 weeks.

The anticipated duration to complete all study-related activities, include data analysis and publications is 4 years (present to 2022). It is anticipated that year 1 and year 2 will involve data collection and year 3 and 4 will involve data analysis, presentations, and publications.,

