#### 8.0 Study Population

*8.1* Inclusion Criteria:

- Female, Aged 17-24 years old
- Diagnosis of major depressive disorder (MDD), Dysthymia, or Other specified/Unspecified Depressive Disorder based on MINI.
- Experiencing current symptoms of depression as indexed by a MADRS-S score  $\geq 13$
- Ability to access the MBT online-based application (e.g., on a personal laptop, tablet, or cell phone)
- Fluent in English
- *8.2* Exclusion Criteria:
  - Any participant with a current diagnosis of epilepsy (must be seizure-free during the 2 years prior to consent to be included)
  - Any participant with a clinically defined neurological disorder or insult indicating, but not limited to, a condition likely to increase the risk of seizure; such as, space occupying brain lesion; history of cerebrovascular accident; transient ischemic attack within two years; cerebral aneurysm; dementia; brain surgery; history of stroke
  - Any participant with an increased risk of seizure for any reason, including prior diagnosis of increased intracranial pressure or history of significant head trauma with loss of consciousness for ≥ 5 minutes.
  - Participants with active or inactive implants (including device leads), including deep brain stimulators, cochlear implants, and vagus nerve stimulators
  - Participants with pre-existing sores or lesions at the site of tDCS or EEG electrode placement
  - A hair style that would impede EEG and tDCS electrode contact (e.g., dread locks)
  - Any participant with a current or possibility of current pregnancy
  - Participants unable to give informed consent.
  - Participation in any investigational drug trial within 4 weeks of the baseline visit

- Clinically significant laboratory abnormality or medical condition, that in the opinion of the investigator would hinder the participant in completing the procedures required by the study
- Currently actively suicidal with intent and plan determined by the C-SSRS at the baseline visit.
- A diagnosis of current or recent substance use disorder (within the past 12 months)
- A diagnosis of Schizophrenia, Bipolar Disorder, or Autism
- Unstable psychotherapy (therapy must be for at least 3 months prior to entry into the study, with no anticipation of change in the frequency or treatment focus of the therapeutic sessions over the duration of the study)

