#### **12.0** Withdrawal of Participants

12.1 Withdrawal Circumstances: Participants who have MRI or tDCS contraindications or participants who experience severe adverse events (e.g., seizure, suicide attempt, acute suicidality with plan of intent) or any unanticipated problem where the principal investigator feels it would be unsafe for the participant to continue may be withdrawn from certain

study activities or withdrawn from the entire study without their consent. In the case of other serious adverse events, the principal investigator or research staff will decide with the participant whether it would be safe or prudent for the participant to continue in the study based on their situation. Participants who experience mild to moderate adverse events (e.g., discomfort or other side effects like headache) will be allowed to discontinue at any point if they choose. Participants withdrawn from study participation due to an adverse event may be replaced to reach intended sample size. Participants will be withdrawn from the study if they appear to be unduly stressed.

- 12.2 Withdrawal Procedures: Participants may withdraw from the study at any time and study staff can withdraw a participant at any time if there are any serious adverse events. In the event of participant withdrawal, research staff may ask participants some questions about the study and/or to participate in some procedures or tests to help participants leave the study safely and/or to collect more information for the study. Information already collected prior to participant withdrawal will still be used. Participants who withdraw or do not qualify for the study after the phone screen may choose to receive referrals for psychological assessments.
- 12.3 Termination Procedures: In the case of a serious adverse event, researchrelated activities may be terminated immediately and appropriate treatment will be provide to the participant (e.g., first aid, emergency treatment, and follow-up care as needed). Care for such injuries will be billed in the ordinary manner to the participant or the participant's insurance company. Following termination, research staff may ask participants some questions about the study and/or to participate in some procedures or tests to help participants leave the study safely and/or to collect more information for the study. Information already collected prior to participant withdrawal will still be used.

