**Suicide/Self-Injury Risk**: The population being researched in this study has a higher risk for suicidal ideation, suicide attempts, and serious injury due to depression. The research team will monitor depression (MADRS-S), suicidal ideation (C-SSRS), and self-harm behaviors (C-SSRS) at baseline, midway through the intervention assessments at the interim assessment, and post-intervention. Answers will be reviewed by the clinical assessor who is trained and supervised by a licensed psychologist. Participants who indicate suicidal ideation or significantly increased self-harm behaviors based on the C-SSRS will be asked to meet with one of the investigators of the study to assess risk.

Participants with suicidal ideation with no plan or intent who agree to a safety plan (either developed with the investigator or a pre-existing safety plan) will be allowed to continue in the study. The investigator will inform parents of the discussion and safety plan (if applicable).

Participants with severe self-harm (requiring stitches or

hospitalization), suicidal ideation with intent, or those who cannot or will not agree to a safety plan will be escorted to the Emergency Room located 1 floor below the Ambulatory Research Center (ARC) in the West Building of the Fairview Riverside Hospital.

**EEG/ECG:** Mild skin irritation may occur at the electrode placement site (e.g., redness).

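### The suicidality and seizure rules disagree: 8.2 admits a state that 17.2 says must end participation, and 12.1 makes optional a discontinuation that 17.2 requires

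*Combined protocol and SAP*

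**What the plan says.** Five parts of the combined protocol and SAP bear on this.

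- **8.2 Exclusion Criteria.** The only suicidality exclusion is "Currently actively suicidal with intent and plan determined by the C-SSRS at the baseline visit". Both elements are needed. Section 5.2 ties the C-SSRS to entry: "This will be administered at baseline for inclusion criteria, at the interim visit, at the post-tDCS and at final assessment visits".
- **13.1, Suicide/Self-Injury Risk.** Monitoring under this heading starts at baseline, and anyone who reports suicidal ideation is asked to meet an investigator. "Participants with suicidal ideation with no plan or intent who agree to a safety plan" are allowed to continue. By contrast, those with severe self-harm, "suicidal ideation with intent, or those who cannot or will not agree to a safety plan will be escorted to the Emergency Room".
- **17.2 Data Safety Monitoring.** "Examples of incidents requiring immediate intervention and discontinuation from the study include active suicidal or homicidal ideation with plan". The same list includes self-harm that needs medical treatment, and a seizure.
- **12.1 Withdrawal Circumstances.** The groups covered include participants with MRI or tDCS contraindications and those with "severe adverse events (e.g., seizure, suicide attempt, acute suicidality with plan of intent"). The operative words, which close the list of groups, are "feels it would be unsafe for the participant to continue may be withdrawn from certain". The sentence goes on to study activities or the whole study, without the participant's agreement.
- **5.3, Randomization.** "Randomization will occur after completion of the 5 at-home MBT sessions before their first tDCS + MBT laboratory visit".

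**The concern.** Staff who meet suicidality or a seizure need one rule. Here the action depends on which section they open.

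At entry, a single baseline C-SSRS can make a participant eligible under 8.2 and, on the same answers, place her under a stop or emergency rule elsewhere. That assessment carries weight: the phone-screen MADRS-S deliberately omits item 9, and 13.1 itself describes this population as being at raised risk of suicidal ideation and attempts.

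On study, 12.1 would allow a participant who has had a seizure to stop some activities and keep others, while 17.2 would end her participation. At stake are the safety of individual participants and uniform handling of the events that most need it.

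**Working it through.** No arithmetic applies, because the plan attaches no figure to these rules. The check sets the sections side by side, case by case.

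**Baseline C-SSRS findings**

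| Finding | 8.2 | 13.1 | 17.2 |
|---|---|---|---|
| Intent and plan | Excluded | Emergency Room | Discontinue |
| Intent, no plan | Not excluded | Emergency Room | Not among the examples |
| Plan, no intent, refuses safety plan | Not excluded | Emergency Room | Discontinue |
| Plan, no intent, accepts safety plan | Not excluded | No outcome stated | Discontinue |
| Ideation, neither plan nor intent, accepts safety plan | Not excluded | Continues | Not among the examples |

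The first and last rows are consistent. The three middle rows are not, because 8.2 lets the participant in while another section diverts or stops her.

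1. *Intent, no plan.* Section 13.1 applies on the day of the baseline assessment. Under 5.3 randomization comes later, after the baseline visits and the home mindful breathing sessions. The Emergency Room rule would therefore normally intervene first. The mismatch is in the wording of 8.2, with a working safeguard behind it.
2. *Plan, no intent, safety plan refused.* Refusal triggers the Emergency Room rule, so the same safeguard works.
3. *Plan, no intent, safety plan accepted.* She fails the 13.1 continuation rule, because she has a plan. She also misses the Emergency Room list, because she has no intent and has agreed to a safety plan. Section 8.2 does not exclude her. Only 17.2 speaks to her case, and it requires discontinuation. This is the real gap.

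**Events on study**

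| Event | 12.1 | 17.2 |
|---|---|---|
| Seizure | Withdrawal optional, may be partial | Discontinuation required |
| Acute suicidality with a plan | Withdrawal optional, may be partial | Discontinuation required |
| Suicide attempt | Withdrawal optional, may be partial | Not among the examples |
| Self-harm needing medical treatment | Not named | Discontinuation required |

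The seizure row is the clearest: both sections name the event, and no reading of C-SSRS categories is needed. Section 12.1 is also uneven within itself. It makes withdrawal mandatory for a participant who seems unduly stressed but optional after a seizure.

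**The case against.** The strongest reply has three parts.

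*An entry criterion and an on-study trigger may differ, and 13.1 covers the difference.* This is largely right for intent without plan. An Emergency Room escort is acute care, and 13.1 does not itself declare anyone ineligible. A reader might infer from 8.2 that participants with suicidal intent would go on to be randomized. The documents do not support that, because 13.1 acts at baseline and randomization follows later. The reply does not reach the plan-only participant who accepts a safety plan, for whom 13.1 gives no instruction.

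*The permissive wording in 12.1 only grants authority to withdraw someone without consent, and 17.2 says when that authority must be used.* The structure of 12.1 lends this some support: severe events are handled without consent, other serious events are decided jointly, and mild to moderate events are left to the participant. Partial withdrawal also makes sense for an MRI contraindication, which sits in the same sentence. But the sentence does not confine partial withdrawal to those cases, so after a seizure it remains open in 12.1 and closed in 17.2.

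*The 17.2 list is only of examples.* True, but the incidents it names are said to require discontinuation, so the conflict stands for them.

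A reader might also infer that the feasibility outcomes in 3.1, enrollment and dropout, are distorted, or that the active-versus-sham comparison is biased. Neither is supported. The plan defines neither *enrolled* nor *dropout*, gives no event frequency and sets no success threshold. Any figure would be the effect of reclassifying one person for any reason, and nothing shows an effect on the comparison between arms. Nor do 8.2 and 17.2 conflict on seizure: 8.2 concerns epilepsy and seizure risk at entry, and 17.2 an event on study.

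**Conclusion.** The rules are wrong as written, in two places. First, 8.2 is looser than 17.2 and 13.1, and in one combination (plan, no intent, safety plan accepted) only the on-study stop rule addresses the participant. Second, 12.1 leaves discretionary and possibly partial what 17.2 requires in full, most plainly for a seizure.

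The ground is patient safety and consistent conduct. No numerical size can be given from the documents. The first conflict assumes that plan and intent can be recorded separately. Section 13.1 treats them as separate elements, but the protocol does not say how C-SSRS answers map onto its rules. It also assumes that investigators follow 13.1 as written at baseline. If in practice they refuse entry to anyone with a plan, the gap is on paper only, and the text should still say so.

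**What to change.** Two wording changes, in one amendment.

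1. **8.2.** In the suicidality criterion, replace *and* with *or*, so that active suicidality with either intent or a plan on the baseline C-SSRS excludes.
2. **12.1.** Add: *Participants with a seizure, a suicide attempt, active suicidal or homicidal ideation with intent or plan, or self-harm that needs medical treatment will be discontinued as 17.2 requires. Partial withdrawal applies only to the other cases, such as MRI contraindications. When clinically safe, these participants are asked to complete the MADRS-S and C-SSRS under the 12.2 exit procedures.* A suicide attempt and intent without a plan are not among the 17.2 examples, so the same list should be repeated there.

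No new procedure is needed: 12.2 already permits exit assessments, and both scales are in the schedule. Eligibility becomes very slightly narrower, and almost everyone newly excluded would already be diverted by 13.1 or 17.2. The investigator loses some discretion, and a discontinued participant gives up her remaining scheduled assessments, although 12.2 keeps the data already collected. If the sponsor prefers to stop the intervention and keep follow-up, 17.2 would have to be reworded to say so. What matters is that both sections give the same instruction.

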## **18.0** Provisions to Protect the Privacy Interests of Participants

### *18.1* Protecting Privacy:

The records of this study will be kept private. In any publications or presentations, participants will not be identified by name or any other identifiable information. Any records, results, or publications related to the study will remain as confidential as possible and will be disclosed only with participant permission. Each participant will be provided with a unique numerical identifier at the beginning of the study in order to protect their actual identification and maintain complete confidentiality.

Mental health professionals are mandated reporters, and as such, are obliged to report alleged or probable abuse, as well as known abuse. Any

concerns about maltreatment will be reported in accordance to the law. If research staff learn that someone (including the participant) is in danger of serious harm), research staff may need to obtain outside assistance.

Only research staff associated with this study and authorized personnel will have access to the records. Research records will be kept in a locked file. Any publications from this study will not include any information that can identify participants. Data will be stored on a password protected electronic database.

A description of this clinical trial will be available on http://www.ClinicalTrials.gov, as required by U.S. Law. This website will not include any information that can identify participants. At most, this website will include a summary of the results.

18.2 Access to Participants: The research team will not access any medical records or other sources of private information outside of information without the participants written consent. HIPAA Authorization will be obtained for all participants.

